## APPENDIX K. SUMMARY OF CHANGES

### Previous Protocol Versions

| Protocol                     | Date             |
|------------------------------|------------------|
| Version 1.0                  | 18 October 2018  |
| Version 1.1 (Germany Only)   | 07 November 2019 |
| Version 1.1.1 (Germany Only) | 20 November 2019 |
| Version 2.0                  | 20 November 2019 |
| Version 3.0                  | 20 November 2019 |
| Version 4.0                  | 11 March 2020    |
| Version 4.1 (Germany Only)   | 12 March 2020    |

The purpose of this version is to remove the [REDACTED] cohort. Minor clerical edits have been made as needed for consistency and clarity throughout the protocol.

### Summary of Protocol Changes:

- Title Page, removed [REDACTED] from the Title Page.  
**Rationale:** [REDACTED] is not being studied in this protocol.
- Synopsis, removed [REDACTED] language from the Synopsis.  
**Rationale:** [REDACTED] is not being studied in this protocol.
- Section 2.1, removed [REDACTED] language from this section and the clinical hypothesis.  
**Rationale:** [REDACTED] is not being studied in this protocol.
- Section 2.2, removed [REDACTED] language, and added language regarding COVID-19 related risks.  
**Rationale:** [REDACTED] is not being studied in this protocol. COVID-19 language added to indicate that no change to the benefit/risk balance for subjects in this study is expected.
- Section 3.1, removed the primary and secondary objectives for the [REDACTED] cohort.  
**Rationale:** To clarify that the [REDACTED] cohort is not being studied in this protocol.
- Section 3.5, revised PK and immunogenicity endpoints to remove [REDACTED].  
**Rationale:** [REDACTED] is not being studied in this protocol.
- Section 3.6, removed [REDACTED] with regard to assessment of changes in cortisol level.  
**Rationale:** [REDACTED] is not being studied in this protocol.
- Section 4.1, revised overall study design, including study schematic, and plan to exclude the [REDACTED] cohort.  
**Rationale:** [REDACTED] is not being studied in this protocol.
- Section 4.2, removed details of study conduct related to [REDACTED].

**Rationale:** [REDACTED] is not being studied in this protocol.

- Section 5.1, removed prior and concomitant medication criteria and expectations for the [REDACTED] cohort.

**Rationale:** [REDACTED] is not being studied in this protocol.

- Section 5.1, removed washout times for prior biologics/tsDMARDs for the [REDACTED] cohort, and shortened duration of treatment with any investigational drug prior to first dose of study drug to 30 days.

**Rationale:** [REDACTED] is not being studied in this protocol. Thirty days is the correct duration; the change to 70 days in the last amendment was made in error.

- Section 5.4, removed reference to [REDACTED] Investigator Brochure and [REDACTED] wash out times before baseline.

**Rationale:** [REDACTED] is not being studied in this protocol.

- Section 5.7, removed details for [REDACTED] cohort dosing.

**Rationale:** [REDACTED] is not being studied in this protocol.

- Section 5.8, removed information about randomization for the [REDACTED] cohort.

**Rationale:** [REDACTED] is not being studied in this protocol.

- Section 6.2, removed drug administration information for [REDACTED]

**Rationale:** [REDACTED] is not being studied in this protocol.

- Section 7.3, removed statistical analyses for efficacy for [REDACTED]

**Rationale:** [REDACTED] is not being studied in this protocol.

- Section 7.4, removed "of each cohort" regarding the Safety Analysis Set.

**Rationale:** [REDACTED] is not being studied in this protocol.

- Section 7.5, removed [REDACTED] from statistical analysis of PK and immunogenicity data.

**Rationale:** [REDACTED] is not being studied in this protocol.

- Section 7.7, removed interim analysis for [REDACTED]

**Rationale:** [REDACTED] is not being studied in this protocol.

- Section 12, reference list updated.

**Rationale:** References that are no longer applicable have been removed.

- [Appendix J](#): revised to remove assessment/procedures related to [REDACTED] cohort.

**Rationale:** [REDACTED] is not being studied in this protocol.

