| Key Eligibility Criteria:                               | 
 
• Subjects or their legally authorized representative must voluntarily sign and date an informed consent, approved by an independent ethics committee (IEC)/institutional review board (IRB), prior to the initiation of any screening or study-specific procedures.
 
• Adult male or female, between 18 and 75 years of age inclusive at Screening.
 
• Diagnosis of RA for > 3 months based on the 1987 ACR classification criteria or 2010 ACR/European League against Rheumatism (EULAR) criteria.
 
• Subject meets the following disease activity criteria: <math>\geq 4</math> swollen joints (based on 28 joint count) and <math>\geq 4</math> tender joints (based on 28 joint count) at Screening and BL Visits; and DAS28(CRP) <math>\geq 3.2</math> at Screening.
 
   |

|  |   |
|--|---|
|  | 
 
Incomplete response to MTX. Subjects must have been on oral or parenteral MTX therapy <math>\geq 3</math> months and on a stable prescription of 15 to 25 mg/week (or <math>\geq 10</math> mg/week in subjects intolerant of MTX at doses <math>\geq 15</math> mg/week) for <math>\geq 4</math> weeks prior to the first dose of study drug. Subject must be expected to be able to continue on stable dose of MTX for the duration of study participation.
 
                     |
| Study Drug and Duration of Treatment: | 
ABBV-3373 (50 mg/mL) and matching placebo, adalimumab (80 mg/0.8 mL) and matching placebo.
 
In the first 12 weeks of treatment, subjects will receive either ABBV-3373 100 mg IV and the matching placebo for adalimumab SC eow or in the control arm the matching placebo for ABBV-3373 IV and adalimumab 80 mg SC eow. At Week 12, the administration of ABBV-3373 will stop (i.e., the last dose of ABBV-3373 will be given at Week 10) to assess the durability of the observed clinical effects up to 24 weeks.
 |
| Date of Protocol Synopsis:            | 04 September 2020   |

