Hypertension is one of the most commonly reported events for GCs in patients, especially with high doses of GCs. Therefore, blood pressure and other vital signs will be monitored during the trial.

Based on the above considerations, the risk to RA patients receiving multiple doses of ABBV-3373 is considered manageable and acceptable. In addition, based on the population and disease being studied and the anticipation that COVID-19 related risks are not expected to differ substantially between study subjects and the broader population of subjects receiving treatment for RA, no change to the benefit/risk balance for subjects in this study is expected.

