### Primary Endpoint Analysis

Analysis of the primary endpoint will be conducted on the FAS based on treatment as randomized.

The primary endpoint is the change from BL in DAS28(CRP) at Week 12. The historical mean and standard deviation of the change from BL in DAS28(CRP) at Week 12 in adalimumab 80 mg eow are estimated to be  $-2.13$  and  $1.35$  respectively based on a meta-analysis of 3 historical adalimumab studies (Studies DE007, DE009, and DE011).

The first comparison in order to achieve the first primary objective of assessing the efficacy of ABBV-3373 is to compare change from BL in DAS28(CRP) at Week 12 in the ABBV-3373 group with  $-2.13$ , the adalimumab 80 mg eow historical mean change from BL at Week 12 based on the meta-analysis. The treatment mean change from BL and 90% confidence interval of ABBV-3373 will be estimated from Mixed Effect Model Repeated Measurements (MMRM) method including up to Week 12 data with treatment group, visits, treatment-by-visit interaction, BL values of the primary endpoint, and stratification factors with observed case (OC) data. The study will be declared positive if the comparison is significant and favoring ABBV-3373.

In order to achieve the second primary objective of comparing clinical efficacy of ABBV-3373 with adalimumab and to test the concept that an anti-TNF ADC has the potential to provide superior efficacy than the traditional anti-TNF antibody in RA, the second comparison is to compare ABBV-3373 with adalimumab for the primary efficacy endpoint with a Bayesian historical data borrowing approach. The same MMRM model as described in the first comparison will be used to estimate in-study mean and standard deviation. Informative normal prior for adalimumab will be determined based on historical adalimumab data and a non-informative prior will be used for ABBV-3373. The prior distributions and estimates from MMRM model will be combined to construct the posterior distributions which will be used for comparison between ABBV-3373 and adalimumab.

If the adalimumab group mean is not comparable with historical adalimumab data, for example, the confidence intervals of the mean based on historical and in-trial data don't overlap, the Bayesian approach based on historical data will not be performed, and the mean difference in change from BL in DAS28(CRP) at Week 12 between the ABBV-3373 group and adalimumab will be estimated only based on in-study data with the MMRM model described above.

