Historical data borrowing will only apply to the primary endpoint.

To address the secondary objectives of assay sensitivity, a synthetic placebo arm will be created with the propensity score matching approach using historical placebo subjects from similar trials with subject-level data. Details will be provided in the SAP.

## Secondary Endpoints and Additional Endpoints Analyses for BL to Week 12

For the first 12 weeks of treatment period, continuous efficacy variables will be analyzed using an MMRM method. Categorical efficacy variables will be analyzed using the Cochran-Mantel-Haenszel (CMH) test controlling for stratification variables. Non-responder imputation (NRI) will be used for primary inference purpose. Observed Case data will be summarized descriptively as a sensitivity analysis.

## Additional Endpoints Analyses up to Week 24

Statistical inference of additional continuous endpoints at each visit up to Week 24 will be conducted using analysis of covariance (ANCOVA) with treatment and stratification factors as the fixed factors and the corresponding BL value as the covariate. Additional categorical efficacy variables up to Week 24 will be analyzed using the same CMH test as for the binary secondary endpoint analysis.

Details on the analyses of the primary and other efficacy endpoints will be provided in the SAP.

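### Section 7.3 fixes non-responder imputation for the binary endpoints to Week 12 without exception, so a visit missed only for pandemic logistics counts as treatment failure for LDA and ACR50

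*Protocol*

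**What the plan says.** The synopsis dates this version "04 September 2020". In the body, COVID-19 appears only in Section 2.2, which states that "COVID-19 related risks are not expected to differ substantially between study subjects and the broader population of subjects receiving treatment for RA". The change log in Appendix K records that addition: "COVID-19 language added to indicate that no change to the benefit/risk balance for subjects in this study is expected". Its only entry for the efficacy analyses is a deletion: "Section 7.3, removed statistical analyses for efficacy for" a cohort no longer studied. No change to a missing-data rule is logged.

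In Section 7.3, the part on secondary and additional endpoints from baseline to Week 12 assigns categorical variables to a stratified CMH test and adds: "Non-responder imputation (NRI) will be used for primary inference purpose". No reason for missingness is exempted. Observed cases serve as a descriptive sensitivity analysis only. Two of the five secondary endpoints in Section 3.3 fall under this rule: LDA (DAS28(CRP) at or below 3.2) and ACR50, both at Week 12.

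For the period up to Week 24 the protocol says: "Additional categorical efficacy variables up to Week 24 will be analyzed using the same CMH test as for the binary secondary endpoint analysis". That sentence names a test and states no imputation rule. The primary endpoint is handled separately, by an MMRM with "BL values of the primary endpoint, and stratification factors with observed case (OC) data".

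**The concern.** Non-responder imputation is usually justified because a missing value often means that the subject left for lack of effect or intolerance. A joint count not done because the site was closed or the subject could not travel carries no such information. The stated rule nevertheless scores it as failure, even for a subject who was responding at Week 10.

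At stake are the size and precision of the Week 12 LDA and ACR50 results. Both rates are pulled down, and the difference between arms shrinks towards zero. With 15 adalimumab subjects, chance imbalance in a handful of logistical misses adds noise that has nothing to do with treatment. The only planned check, a descriptive observed-case summary, gives no inferential result to set beside the main one.

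**Working it through.** **The plan's own figures, and whether the rule touches them.** Inputs are from Section 7.3: SD 1.35, changes of -2.13 for adalimumab and -2.769 to -2.982 for ABBV-3373, and 30 and 15 subjects.
- One-sample t-test, one-sided 0.05: 81.2% and 95.8% (stated 81% to 96%).
- Bayesian comparison with prior N(-2.13, 0.246²): 66.4% and 88.6% (stated 66% to 88%), with type I error 0.027 (stated about 0.03).
- In-study data only: 43.2% and 62.5% (stated 43% to 63%).

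All reproduce. All concern the continuous endpoint, so non-responder imputation enters none of them.

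**Assumptions.** The protocol gives no binary response rates, baseline score or missed-visit rate. Assumed here: baseline DAS28(CRP) 5.7 for every subject, and a share m of 5%, 10% or 20% of Week 12 visits missed for logistics, equal in both arms and unrelated to response.

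**True LDA rates.** p = Φ((3.2 - mean at Week 12)/1.35).
- ABBV-3373: mean 5.7 - 2.982 = 2.718, so p = Φ(0.357) = 63.9%.
- Adalimumab: mean 5.7 - 2.13 = 3.570, so p = Φ(-0.274) = 39.2%.
- Difference: 24.7 points (24.75 before rounding).

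**Under non-responder imputation** the expected rate is p(1-m), so the expected difference is 24.75 × (1-m).

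| m | ABBV-3373 | Adalimumab | Difference |
|---|---|---|---|
| 5% | 60.7% | 37.2% | 23.5 |
| 10% | 57.6% | 35.3% | 22.3 |
| 20% | 51.2% | 31.4% | 19.8 |

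**Added noise.** The departure of the reported difference from its complete-data value has mean square Σ pm(1-pm)/n over the two arms, plus (m × difference)². At m = 10%: 0.0639 × 0.9361/30 + 0.0392 × 0.9608/15 + 0.0247² = 0.00199 + 0.00251 + 0.00061 = 0.0051, so the root mean square is about 7.2 points. The same formula gives about 5.0 at 5% and 10.5 at 20%.

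Simulation (1,500 runs per setting, with a further assumed Week 10 to 12 correlation of 0.8) gave 5.1, 7.0 and 10.5 points under non-responder imputation. Multiple imputation on arm and Week 10 score gave 2.7, 3.9 and 5.8. Mean differences were 23.1, 22.4 and 19.2 against 24.4, 24.8 and 24.5.

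**One visit.** The largest shift is 1/15 = 6.7 points for adalimumab and 1/30 = 3.3 points for ABBV-3373, reached only if the subject would have responded. On the LDA rates above, the expected drop per miss is 39.2/15 = 2.6 and 63.9/30 = 2.1 points.

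**ACR50, illustration only.** With assumed true rates of 60% and 40%, the 20-point difference becomes 19, 18 and 16 points. Approximate two-sided power is 24% with nothing missing. It is 22%, 20% and 17% under non-responder imputation, against 23%, 22% and 20% on observed cases.

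**The case against.** The strongest reply is that this is SAP content. Sections 7.1 and 7.3 leave the details to the SAP, which is not at hand, and an exception by reason for missingness is the sort of detail an SAP often sets. What stands is that the SAP may already contain it. But the point is a rule that the protocol states without qualification, not a gap. An SAP exception would depart from that sentence unless the two are aligned, and it needs the reason for each missed visit to be collected while the trial runs.

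Several stronger readings are tempting, and the documents do not support them.
- A reader might infer that Section 7.3 contradicts itself, because a missing DAS28(CRP) is left unobserved in the MMRM while LDA, a cut of the same score, calls it failure. Pairing an MMRM for a continuous score with non-responder imputation for its dichotomised form is common and is no contradiction.
- A reader might infer that the duration-of-effect results up to Week 24 are understated in the same way. The text for that period fixes only the CMH test, so how missing values enter is not stated there.
- A reader might take the change log as evidence that missing data were mishandled. Its COVID-19 line concerns benefit and risk only.
- A reader might fear bias in favour of one arm. That needs unequal missingness, of which the protocol gives no sign. Equal, unrelated missingness only attenuates the difference.

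The simulation also flatters multiple imputation somewhat: it imputes from the same normal model that generated the data, under completely random missingness, and covers LDA only. Imputing ACR50 components from 30 and 15 subjects, then pooling stratified CMH results, is harder and was not tested.

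**Conclusion.** The point holds, within limits. As written, the rule turns a Week 12 visit missed only for pandemic logistics into a treatment failure for LDA and ACR50. If such misses are unrelated to response, both rates and the difference shrink by (1-m). On the LDA assumptions the loss is about 1 to 5 points for 5% to 20% missing, and the error added by missed visits is nearly twice that under multiple imputation (7.0 against 3.9 points at 10%).

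The factor (1-m) needs only equal missingness unrelated to response. The point values also rest on the assumed baseline and missed-visit rates, and the comparison with multiple imputation on the assumed correlation. The protocol supplies none of these, nor how many subjects still awaited Week 12 in September 2020. It would be wrong to conclude that the trial's main result is at risk: the primary endpoint, both success criteria and the sample size stand as they are.

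**What to change.** Qualify the sentence in Section 7.3 along these lines:

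- Non-responder imputation applies to categorical values missing for any reason other than COVID-19 logistical restrictions.
- Values missing for those restrictions are multiply imputed under missing at random from treatment, baseline and earlier visits of the underlying score. Keep the model simple, given 30 and 15 subjects. The CMH results are combined over imputations.
- Non-responder imputation of all missing values is reported as a sensitivity analysis.

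Limit the exception to logistics. Treating values missing because of COVID-19 infection as ignorable is debatable in a trial where Section 6.1 lists serious infections among the adverse events of special interest.

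Record on the eCRF whether a missed visit was due to COVID-19 logistics. State the same missing-data rule for the categorical endpoints up to Week 24, where only the test is named. If the SAP already has the exception, aligning the protocol sentence with it is enough.

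The cost is protocol and SAP wording, one eCRF field and one imputation step, which is more laborious for ACR50 than for LDA. The downside is a model-based imputation for a few subjects in a small trial. The primary analysis does not change.

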## Summary of Operations Manual Changes:

- Title Page, removed [REDACTED] from Title Page.

**Rationale:** [REDACTED] is not being studied in this protocol.

- Section 1, added section description for clarity, and removed [REDACTED] from Pharmacokinetic Lab section.  
**Rationale:** [REDACTED] is not being studied in this protocol.
- Section 2.1, removed study activities for [REDACTED].  
**Rationale:** [REDACTED] is not being studied in this protocol.
- Section 3.5, removed sections for PK and immunogenicity sampling for [REDACTED].  
**Rationale:** [REDACTED] is not being studied in this protocol.
- Section 3.6, removed biomarker sampling for [REDACTED].  
**Rationale:** [REDACTED] is not being studied in this protocol.
- Section 3.12, removed clinical laboratory testing for the [REDACTED] cohort.  
**Rationale:** [REDACTED] is not being studied in this protocol.
- Section 5.1, removed [REDACTED] for SUSAR reporting.  
**Rationale:** [REDACTED] is not being studied in this protocol.
- Section 6.1, removed section for [REDACTED] treatment administration.  
**Rationale:** [REDACTED] is not being studied in this protocol.
- Section 6.2, removed information on for [REDACTED] drug supply, storage, and disposition.  
**Rationale:** [REDACTED] is not being studied in this protocol.
- Section 6.3, removed the section for method of assigning subjects to treatment groups for the [REDACTED] cohort.  
**Rationale:** [REDACTED] is not being studied in this protocol.
- Section 6.4, removed the section for timing of study drug in the [REDACTED] cohort.  
**Rationale:** [REDACTED] is not being studied in this protocol.

## APPENDIX L. OPERATIONS MANUAL
